The melatonin will be administered rectally in a fluid, followed by plasma samples over the following 24 hours. The melatonin formulation applied for rectal administration will be a 2.5 ml fluid containing 25 mg of melatonin. The delivery of the fluid is to be performed via an enema. The subjects will be asked to defecate, if possible in the morning, prior to the administration of melatonin.

Study session 3: Intravesical administration

The melatonin/dimethyl sulfoxide (DMSO) aqueous solution will be administered intravesically, followed by plasma samples over the following 24 hours. The melatonin used in the study will be applied intravesically through a catheter at a dose of 25 mg in 50 ml of a solution of 50% (w/w) DMSO in water, the solution containing melatonin at a concentration of 0.5 mg/ml. The subjects will be asked not to consume fluids three hours prior to the start of the study day, and will be asked to void their bladder prior to administration of melatonin.

Study session 4: Vaginal administration

The vaginal suppository containing melatonin will be administered vaginally, followed by plasma samples over the following 24 hours. The melatonin used in the study will be applied at a dose of 25 mg in a suppository (Witepsol S58) vaginally, by the participant themselves.

Study session 5: Transdermal administration

The melatonin will be administered topically as 1 g of a 2.5% (w/w) melatonin cream over a skin area of 20 x 20 cm (400 cm²), followed by plasma samples over the following 48 hours. The dose of melatonin used in the study will thus be 25 mg. The participants will be asked to refrain from using any other creams or lotions one day prior to the study session, and for the following 48 hours.

Outcomes

The outcomes are identical for four of study sessions of the trial (intravenous, rectal, intravesical, and vaginal). The transdermal study session will have a follow-up of 48 hours rather than 24 hours. These differences are outlined below.

Primary outcome

Plasma concentration of melatonin at baseline, 0 min, 10 min, 20 min, 30 min, 40 min, 50 min, 1 hour, 2 hours, 3 hours, 4 hours, 6 hours, 8 hours, and 24 hours. Blood samples are drawn from a peripheral venous catheter within the first 8 hours, and the 24-hour samples will be taken as a single venipuncture. Each blood sample will have a volume of 6 ml, totaling 84 ml for each of the four first study sessions. For the blood samples drawn from a peripheral venous catheter, 4 ml of blood

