The volunteers can withdraw their consent at any point during the trial. The dropout criteria of the study are if a subject at some point during the study starts to fulfill any of the exclusion criteria, or if a subject is unable to participate in all five study sessions. Furthermore, the investigator can at any point exclude participants from the trial, if the investigator deems it necessary for the safety of the participant. The reason for a subject withdrawing their consent will be reported in the CRF. Data from dropouts will not be used in the statistical analysis.

Conclusion of the study

Each volunteer will have concluded the study after finishing all five study sessions. A total of ten subjects will be included in the study. In case of dropouts, the study will be concluded after a total of eight subjects have completed the study. If more than two subjects drop out, we will include further subjects until a minimum of eight subjects have completed the study.

Handling of melatonin formulations

Storage

Melatonin alcohol/saline solution

Dry melatonin will be packaged according to EU GCP/GMP-guidelines in containers with 25 mg melatonin. All containers with dry melatonin will be given a batch number. The 99.9% ethanol solvent will be packaged in ampoules and also be given a batch number. The melatonin, the 0.9% saline, and the 99.9% ethanol solvent will be acquired via Skanderborg Apotek.

Melatonin rectal fluid

The melatonin fluid, consisting 25 mg of melatonin dissolved in 2.5 mL of a 20% w/w glycofurol, and 40% w/w DMSO solution in water. This fluid has been demonstrated by Bioneer A/S to have no degradation of melatonin while being stored at 25°C for 45 days. Therefore, the fluid will be stored at room temperature. This fluid will be produced and packaged by Glostrup Apotek, according to GMP-guidelines. The fluid will be packaged in single dose mini enemas, and each box will contain 12 mini enemas.

Melatonin/DMSO solution

The melatonin will be dissolved into a 50/50% w/w DMSO and water solution at a concentration of 0.5 mg/g. This solution has been demonstrated by Bioneer A/S to have no degradation of melatonin while being stored at 25°C for 45 days. Therefore, the fluid will be stored at room temperature. The fluid will be packaged in single dose vials (50 ml), and each box will contain 12 vials. The melatonin/DMSO solution will be produced and packaged by Skanderborg Apotek, according to GMP-guidelines.

Melatonin suppository

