The 25 mg melatonin will be administered as 2.5 ml of a 10 mg/ml fluid, as an enema via a plastic tube with a stud with an opening. The fluid used will be a 20% w/w glycofurol and 40% w/w DMSO aqueous solution. The plastic stud on the enema will be inserted into the rectum, and the fluid will be administered as a bolus. The enema is then removed, and a clock is started to measure time from administration.

Study session 3: Intravesical administration

50 ml of melatonin 0.5 mg/ml solution in the 50% (w/w) DMSO/water solvent will be aspirated into a 50 ml syringe, totaling 25 mg melatonin. A Clean Intermittent Catheter (CIC) is inserted into the subject through the urethra, into the bladder, and the bladder of the subject will be emptied. Afterwards, the 50 ml syringe will be connected to the CIC, and the 50 ml solution will be administered into the subject at a rate of 25 ml/minute over 2 minutes. The catheter is then removed, and a clock is started to measure time from administration. Subjects will be required not to void their bladder until after the 1-hour blood sample has been collected.

Study session 4: Vaginal administration

The 25 mg of melatonin will be administered in a suppository, vaginally. The subjects will be handed a suppository, which they will themselves take out of the blister pack, and insert vaginally. As soon as the suppository is administered, a clock is started to measure time from administration.

Study session 5: Transdermal administration

The melatonin cream will be administered over a skin area of 20 x 20 cm. This area will be measured and outlined with a marker on the subject's chest, starting at the medial end of the left clavicle, horizontally towards the mid-axillary line, and vertically parallel to the sternum towards the stomach. Afterwards, 1g of melatonin cream will be measured on a scale, on a piece of non-stick paper by the investigator. The subject will then apply the melatonin cream over the 20 x 20 cm area. The subject will be wearing a glove and only use the fingertips in order to maximize the dose applied. After the melatonin cream has been adequately applied, a clock is started to measure time from administration.

Adverse reactions

Adverse reactions to melatonin

Melatonin is non-toxic in both physiological and pharmacological doses [35]. In mice, rabbits, cats, and dogs, melatonin doses of 800 mg/kg administered intravenously demonstrated no toxicity [36].

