DMSO is regularly used in the treatment of interstitial cystitis, either as monotherapy, or serving as a vehicle for anti-inflammatory agents [48-50]. DMSO has previously been applied as a solvent for intravesical drug administration in the treatment of bladder cancer [51, 52]. An adverse reaction of DMSO is a garlic-like breath odor and taste, due to pulmonary elimination of a small percentage of the DMSO as dimethyl sulfide. One study demonstrated that up to 48% of patients with interstitial cystitis reported adverse reactions, including urethral irritation and nausea [49]. However, these adverse reactions are self-limiting, lasting up to 24-48 hours [48-50].

Adverse reactions of glycofurol

Glycofurol has previously been used as a solvent for rectal administration of methadone [53, 54]. Furthermore, glycofurol is used as an ingredient in Stesolid® (diazepam) rectal fluid [55]. Glycofurol is generally perceived as a non-toxic and non-irritant material, being nevertheless irritating if injected undiluted [56]. In this study, the glycofurol will be diluted to a 20% w/w

glycofurol and 40% w/w DMSO in water, the solution containing 10 mg/g melatonin. Therefore any irritating effects from the glycofurol should be avoided.

Adverse effects of plasma sampling

During the study a total of 136 ml of blood will be sampled from the subjects per study session the first four study sessions (intravenous, rectal, intravesical, and vaginal). A total of 122 ml of blood will be sampled from the subject during the transdermal study session. The drawn volume is in no way a health risk for the subjects. Drawing of blood samples can leave the subjects with small hematomas and the patients will feel a small sharp scratch when the needle is inserted.

Adverse events

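### The intravesical solution is specified per millilitre where it is given but per gram where it is produced, which leaves D in the bioavailability formula uncertain; the rectal fluid shows a weaker instance

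*Combined protocol and SAP*

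**What the plan says.** All references are to the combined protocol and SAP.

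**Intravesical solution.** Study course, Study session 3, has "the solution containing melatonin at a concentration of 0.5 mg/ml". Administration, Study session 3, agrees: "50 ml of melatonin 0.5 mg/ml solution in the 50% (w/w) DMSO/water solvent will be aspirated into a 50 ml syringe, totaling 25 mg melatonin". Handling of melatonin formulations, Melatonin/DMSO solution, uses a different basis: "The melatonin will be dissolved into a 50/50% w/w DMSO and water solution at a concentration of 0.5 mg/g". That same paragraph sets the fill by volume, as one-dose vials of 50 ml, and names the producing pharmacy.

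**Rectal fluid.** Study course, Study session 2: "The melatonin formulation applied for rectal administration will be a 2.5 ml fluid containing 25 mg of melatonin". Handling of melatonin formulations, Melatonin rectal fluid: "The melatonin fluid, consisting 25 mg of melatonin dissolved in 2.5 mL of a 20% w/w glycofurol". Administration, Study session 2: "The 25 mg melatonin will be administered as 2.5 ml of a 10 mg/ml fluid". Only Adverse reactions of glycofurol is per gram: "the solution containing 10 mg/g melatonin".

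**Use in the analysis.** In Statistics, bioavailability f is the ratio of extravascular to intravenous AUC, each scaled by its dose D. D is defined only as the dose given. The section does not say whether that is the nominal 25 mg or a measured content.

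**The concern.** The same number appears per millilitre and per gram for one fluid, and the two are interchangeable only if a millilitre weighs exactly one gram. The solvents are 50% w/w DMSO in water (intravesical) and 20% w/w glycofurol with 40% w/w DMSO in water (rectal). The plan gives no density, fill weight or batch content for either, and both are given by volume.

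The intravesical case carries the weight, because its per-gram figure stands in the text that describes how the product is made and packed. A pharmacy that follows that text as written, and fills 50 ml, would deliver 25 mg only at a density of 1.00 g/ml.

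At stake is D, a direct multiplier in f. An error in D is the same proportion in every subject, so averaging over eight to ten subjects does not reduce it and the reported spread does not reveal it. It would also shift the affected route relative to the suppository, which is a 25 mg unit, and the cream, which is specified per gram and weighed.

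**Working it through.** **Inputs from the plan**
- Intravesical: 50 ml; 0.5 mg/ml (Study course; Administration) or 0.5 mg/g (Handling).
- Rectal: 2.5 ml; 10 mg/ml (Administration) or 10 mg/g (Adverse reactions of glycofurol).
- Stated dose by each route: 25 mg.

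**Input not in the plan**
- Density ρ in g/ml. Assumed range: 1.00 to 1.10.

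**Step 1. Reproduce the stated dose on the per-millilitre basis.** Dose = volume × mg/ml.
- Intravesical: 50 × 0.5 = 25 mg.
- Rectal: 2.5 × 10 = 25 mg.

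Both match the plan exactly.

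**Step 2. Same volumes on the per-gram basis.** Dose = volume × ρ × mg/g.
- Intravesical: 50 × ρ × 0.5 = 25ρ mg.
- Rectal: 2.5 × ρ × 10 = 25ρ mg.

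The two bases give the same dose only at ρ = 1.00.

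**Step 3. Effect on f.** D for the extravascular route is in the denominator. If 25ρ mg was given but 25 mg is entered, reported f ÷ true f = 25ρ ÷ 25 = ρ.

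| Assumed ρ (g/ml) | Dose if made per gram (mg) | Relative overstatement of f | True f of 20% reported as | True f of 50% reported as |
|---|---|---|---|---|
| 1.00 | 25.0 | 0% | 20.0% | 50.0% |
| 1.02 | 25.5 | 2% | 20.4% | 51.0% |
| 1.05 | 26.25 | 5% | 21.0% | 52.5% |
| 1.10 | 27.5 | 10% | 22.0% | 55.0% |

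The 20% and 50% are illustrative only. A density below 1.00 would reverse the sign of the error.

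**Step 4. Which sections conflict, by fluid.**

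| Section | Intravesical | Rectal |
|---|---|---|
| Study course | 0.5 mg/ml | 25 mg in 2.5 ml |
| Handling (storage and production) | **0.5 mg/g**, 50 ml vial | 25 mg in 2.5 mL |
| Administration | 0.5 mg/ml | 10 mg/ml |
| Adverse reactions of glycofurol | – | **10 mg/g** |

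For the intravesical solution the production text conflicts with the two sections on use. For the rectal fluid the production text agrees with them, and the odd one out is a descriptive sentence about irritation.

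**The case against.** A reader might infer that the plan states contradictory milligram doses. It does not. Every rectal and intravesical dose it states is 25 mg, and Step 1 reproduces that figure. A different dose has to be inferred, and only if production followed the per-gram figure. If the pharmacy fills to a content of 25 mg, D has no error. This objection stands, and it limits the point to the concentration basis.

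A reader might also treat the two fluids as equally exposed. The documents do not support that. For the rectal fluid, an error would require the pharmacy to set aside its own formulation text and work from the safety sentence. This also stands: the rectal instance is secondary.

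Third, the effect may be immaterial. The plan has no power calculation and no equivalence margin, test or threshold for f, and a shift from 20% to at most 22% would probably not change a qualitative view of a route. The Administration text for the intravenous session has a potentially larger problem of its own: 25 mg in 4 ml ethanol and 46 ml saline is 25 ÷ 50 = 0.5 mg/ml, yet the same sentence gives 1 mg/ml. That bears on the intravenous D, which scales f for every route. It needs separate reconciliation. It makes this point smaller by comparison but does not remove it.

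Finally, Statistics does not prescribe a nominal 25 mg for D, and documented content is not exactly the delivered amount, because residue in the enema, syringe or catheter is not captured. Both are fair. But the plan leaves the choice of D open while giving two concentration bases, and documented content would at least settle the density question.

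**Conclusion.** The point holds as a unit inconsistency, mainly for the intravesical solution, with a possible proportional error in f. The size is 0% to 10% in relative terms (25.0 to 27.5 mg against a nominal 25 mg). That rests on three conditions: the fluid is made per gram and dispensed by volume, D is entered as 25 mg, and the density lies in the assumed range of 1.00 to 1.10 g/ml. Nothing in the documents fixes the density, so neither end of the range is established.

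Severity is low. The point is more than clerical because the intravesical per-gram figure is a production specification that feeds a term of the bioavailability formula. No view is taken on which concentration is right.

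**What to change.** 1. Intravesical solution: reconcile the Melatonin/DMSO solution text under Handling of melatonin formulations with Study session 3 under Study course and under Administration, so that the fluid has one unit basis.
2. Rectal fluid: reconcile Adverse reactions of glycofurol with Study session 2 under Study course and under Administration, and with the Melatonin rectal fluid text under Handling, in the same way.
3. Statistics: state that D for the rectal and intravesical routes is the pharmacy's documented content per ml times the volume given, rather than an assumed nominal 25 mg.

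The cost is wording, plus one figure per fluid (content per ml, or the density needed to derive it) from the producing pharmacy. The design, sampling and sample size do not change.

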Before any studies investigating the radioprotective effects of locally administered melatonin can be undertaken in humans, it is imperative that the pharmacokinetic properties of melatonin are investigated when administered in this way. No previous studies investigating the pharmacokinetics of vaginal, intravesical, or rectal administration of melatonin have been performed [23]. The few studies investigating transdermal administration of melatonin have been insufficient [24-26]; only one study has been able to estimate a $T_{1/2}$, and only in two volunteers [27], and no studies have investigated transdermal bioavailability [23].

Study design

Objective

The aim of the study is to determine the pharmacokinetic properties of, and possible adverse reactions of, melatonin when administered intravenously, rectally, intravesically, vaginally, and transdermally, in healthy female volunteers.

Design

This study is a crossover study, including five individual study sessions investigating five different routes of administration of melatonin. Four of the study sessions (intravenous, rectal, intravesical, and vaginal) will consist of one study day and one plasma sample the following day. The transdermal application will consist of one study day, followed by plasma samples at 24 and 48 hours following application. Between each study session, the subjects will have a washout period of a minimum of 7 days. The study will include a total of ten healthy female volunteers.

The subjects will participate in study sessions in the following order: intravenous, rectal, intravesical, vaginal, and transdermal administration. The study will be concluded after the

48-hour plasma sample after transdermal administration. Should a participant be menstruating at the time of the vaginal administration study session, the session will be postponed for one week.

Study course

Study session 1: Intravenous administration

The melatonin will be administered intravenously, followed by plasma samples over the following 24 hours. The intravenous melatonin will be dissolved in an ethanol/saline solution (2 ml 99.9 % ethanol/23 ml 0.9 % saline) containing 25 mg of melatonin. The infusion of melatonin will be performed over 10 minutes, the infusion rate being 2.5 mL per minute.

Study session 2: Rectal administration

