The subjects will be questioned about adverse events during each study session and at the 24-hour plasma sample (as well as at 48 hours for the transdermal study session). We have defined five pre-specified self-reported symptoms (fatigue, confusion, depressed mood, or headache), based on the most commonly reported adverse reactions of melatonin available in the literature [See attached Investigators Brochure]. Volunteers will also be asked to report additional symptoms of adverse effect, if any. Both adverse reactions and adverse events will be reported in the CRF. An adverse reaction is defined as harm or unwanted reaction to a drug, no matter the dosage. An adverse event is defined as any medical event in a patient or healthy volunteer in a clinical trial after treatment with a drug, without any necessary connection between the treatment and the undesirable event.

Serious adverse events (SAE) are defined as any medical event that result in death, are life-threatening, lead to hospitalization, result in disability or permanent damage, or any other important medical event. All serious adverse events will be registered and reported to the Danish

Medicines Agency (Lægemiddelstyrelsen) and the Danish Committee on Health Research Ethics (Videnskabetisk Komité) in a final report.

Serious adverse drug reactions (SARs) will be reported annually (most likely irrelevant to this study, as it will not continue for a full year).

Suspected unexpected serious adverse reactions (SUSARs) will be reported immediately to the Danish Medicines Agency and the Danish Committee on Health Research Ethics.

Summary of Product Characteristics and Investigators Brochure (both are attached to this document) will be used to evaluate SUSARs. Adverse event registration will commence on the first study day and be finalized after the last study day. In case of serious adverse reactions the sponsor will decide if the study is to be terminated.

Setting

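### For completers, adverse-event registration ends about 48 hours after the cream but stays open at least 7 days after each other route; scheduled questioning is unequal the other way, so counts by route are not comparable.

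*Combined protocol and SAP*

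**What the plan says.** The closing rule is in the section Adverse events: "Adverse event registration will commence on the first study day and be finalized after the last study day". It is tied to the calendar of the study, not to each dose.

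The timetable is in Study design, Design. The order is the same for everyone: "The subjects will participate in study sessions in the following order: intravenous, rectal, intravesical, vaginal, and transdermal administration". The spacing is also set: "Between each study session, the subjects will have a washout period of a minimum of 7 days". The cream session has its own structure: "The transdermal application will consist of one study day, followed by plasma samples at 24 and 48 hours following application". The study ends after the "48-hour plasma sample after transdermal administration". If a subject is menstruating when the vaginal session is due, "the session will be postponed for one week"; no change of order is mentioned.

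Conclusion of the study confirms the end point for each person: "Each volunteer will have concluded the study after finishing all five study sessions". No visit, call or message after that is described.

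The section Adverse events also schedules active questioning: "The subjects will be questioned about adverse events during each study session and at the 24-hour plasma sample (as well as at 48 hours for"; its closing words, not quoted here, name the cream session.

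**The concern.** The stated objective covers possible adverse reactions as well as pharmacokinetics, for all five routes. Because registration follows the calendar and the cream always comes last for completers, the period in which a reaction can be registered depends on the route by construction. With a fixed order, the short period falls on the same route in every completer and cannot average out.

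Two things are at stake. First, an event that begins on day 3 or later after the intravenous, rectal, intravesical or vaginal dose lies inside the registration period, and the subject is still due to return. The same event after the cream lies outside it, and she is not due back. Second, any table of adverse events by route would set side by side counts collected over different periods and with different amounts of questioning.

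**Working it through.** No figure in the plan can be reproduced here, since the protocol gives no length of safety follow-up by route. The check is timeline arithmetic for a completer.

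**Inputs.** Fixed order with the cream fifth, minimum gap of 7 days, and end of study 48 hours (2 days) after the cream (all from Design); no contact after the fifth session (Conclusion of the study); questioning to 24 hours, or 48 hours for the cream (Adverse events).

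**Step 1: minimum time under registration.** With gap *g* between doses, dose *i* falls on day *g*(*i* − 1), and registration closes on day 4*g* + 2. Time open after dose *i* is therefore 4*g* + 2 − *g*(*i* − 1). The protocol does not say where the washout starts, so two counts are shown: from dose to dose (*g* = 7, closing on day 30), and from the 24-hour sample to the next dose (*g* = 1 + 7 = 8, closing on day 34).

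| Route | Days to next dose (g = 7 / 8) | Days to closure (g = 7 / 8) | Last scheduled question |
|---|---|---|---|
| Intravenous | 7 / 8 | 30 / 34 | 24 h |
| Rectal | 7 / 8 | 23 / 26 | 24 h |
| Intravesical | 7 / 8 | 16 / 18 | 24 h |
| Vaginal | 7 / 8 | 9 / 10 | 24 h |
| Transdermal | none | 2 / 2 | 48 h |

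The fair comparison is time to the next dose, because later events can no longer be assigned cleanly to the earlier route. That gives at least 7 days (168 hours) for each of the first four routes and 48 hours for the cream: 48/168 = 29% of the first week, or a period 168/48 = 3.5 times shorter. A one-week postponement of the vaginal session would lengthen the gap after the intravesical dose to 7 + 7 = 14 days and would not change the cream's 2 days.

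**Step 2: what is actively asked.** The last scheduled question comes at 24 hours for four routes and 48 hours for the cream, so the cream is followed 48/24 = 2 times as long. Nothing is scheduled between the 24-hour sample and the next session, and the protocol does not say that the next session asks about the interval. The 7 days for the first four routes are therefore an open period for spontaneous reports or recall, not active follow-up.

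**Step 3: what all routes share.** The only period with scheduled questioning for every route is the shorter of the two, 0 to 24 hours.

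**Step 4: what cannot be computed.** The protocol gives no rate or time of onset for reactions beyond 48 hours, so the number of events missed is unknown.

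**The case against.** The strongest reply is that scheduled questioning, not the nominal registration period, determines most of what is recorded, and by that measure the cream is followed longer. This stands. A reader might infer that the cream would look better tolerated because its period is shorter. The documents do not support that: events solicited between 24 and 48 hours are collected for the cream alone, which could make it look worse, and the two imbalances cannot be netted off.

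A reader might also take the closing sentence literally and infer that registration ends with the cream study day itself, whose last sample is at 16 hours. The same section requires questioning at 48 hours, so that reading contradicts the protocol's own schedule. About 48 hours is the reading that fits, although it is inferred from the end-of-study wording and not stated as a closing time. Nor does reading the last study day as that of the whole trial help: each volunteer has concluded after her own fifth session.

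It can also be said that the Statistics section plans no contrast of adverse events between routes, that there are only eight to ten subjects, and that no source for late reactions is given. All true, and these points limit the weight of the issue. The objective nevertheless names adverse reactions for every route, so results by route are the natural report. The 24 to 48 hours given in Adverse reactions of DMSO as the duration of vehicle reactions come from intravesical use in interstitial cystitis and say nothing on the time course of skin reactions to this cream.

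Finally, serious events are all to be registered, and unexpected serious reactions reported at once, with no end date of their own. It would therefore go too far to say that a late serious event would be left out. What stands is that no contact or rule after the 48-hour sample brings it in.

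**Conclusion.** The point holds as a gap in safety follow-up after the final dose and as a lack of comparability between routes. For completers, registration is open at least 7 days after each of the first four doses and about 48 hours after the cream, while the last scheduled question comes at 24 hours and 48 hours respectively. The 3.5-fold difference describes the nominal registration period only; it is not a difference in active ascertainment or in events captured. The direction of any net bias is unknown.

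This rests on three assumptions: that registration closes with the 48-hour sample, that no unwritten follow-up exists, and that the subject completes all sessions. For a subject who drops out earlier, the last session is a different one and the protocol does not say when her registration closes. The pharmacokinetic outcomes are not affected.

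**What to change.** 1. In Adverse events, replace the calendar rule with closure at a set time after each subject's last dose, for example 7 days to match the minimum washout, and state that this applies to dropouts too. The 7 days are a convenience for comparability, not a figure with a safety rationale in the protocol.
2. Reconcile this with the end-of-study wording in Design and in Conclusion of the study, so that the last sample and the end of safety follow-up are distinguished.
3. Ask one identical question about events since the last dose, with date of onset, at the start of sessions 2 to 5 and by one telephone or e-mail contact about day 7 after the cream. A contact after the cream alone would only create a new imbalance.
4. In Statistics, state that adverse events are summarised by route over a common post-dose window (0 to 7 days, assigned to the most recent dose). If the contact is not added, restrict the summaries by route to 0 to 24 hours and list later events separately.

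Cost: with ten subjects, about ten short contacts and 10 × 4 = 40 added questions at visits already planned, plus the edits to the text. No extra visit, blood sample or staff is needed.
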